Study Title: Umbilical Trocar Site Is the Usual Suspect for Trocar Hernia After LaparoscopicCholecystectomy: A Prospective StudyNCT ID: Not yet assigned.

Date: April 15, 2025

CLINICAL STUDY REPORT (CSR)

Study Title: Umbilical Trocar Site Is the Usual Suspect for Trocar Hernia After Laparoscopic
Cholecystectomy: A Prospective Study
Study Type: Prospective, randomized controlled trial
Study Duration: April 15, 2022 – June 15, 2024
Study Location: Umraniye Training and Research Hospital, Department of General Surgery
Principal Investigator: Ass. [name]. [name]
ClinicalTrials.gov ID: Not yet assigned

1. Study Synopsis

Objective:

To evaluate whether the site of gallbladder retrieval (umbilical vs. epigastric) affects the incidence of trocar site hernia (TSH) following laparoscopic cholecystectomy (LC), and to identify risk factors for TSH.

Design:

Prospective, randomized, single-blind, controlled study with two parallel arms.

Participants:

110 patients undergoing elective LC for gallstone disease were randomized. After accounting for conversions and loss to follow-up, 100 patients (50 in each group) were included in the final analysis.

Intervention:

Standard 4-port LC performed. Gallbladder retrieved via either:

Group U: Umbilical trocar (10 mm)

Group E: Epigastric trocar (10 mm)

Primary Outcome:

Incidence of trocar site hernia at 12-month follow-up.

Secondary Outcomes:

Gallbladder retrieval time

Postoperative pain scores (VAS at 6 and 24 hours)

Risk factor analysis for TSH development

Key Results:

TSH occurred in 12% (6/50) of umbilical group and 10% (5/50) of epigastric group (P = 1.00).

All hernias were located at the umbilical site.

Epigastric retrieval was faster (P = 0.013) but associated with more early pain (P = 0.027).

Fascial widening was the only independent risk factor for TSH (OR = 4.08, P = 0.05).

2. Study Design

Randomization:

Performed via the Alea Randomisation mobile app. Allocation was sealed and revealed intraoperatively before specimen retrieval.

Blinding:

Patients were blinded. Surgeons were not blinded due to the nature of the procedure, but were unaware of group allocation until extraction.

Surgeon Consistency:

All surgeries were performed by three experienced general surgeons using standardized techniques.

Antibiotic Prophylaxis:

Intravenous cefazolin 2 g administered preoperatively.

3. Inclusion / Exclusion Criteria

Inclusion:

Age ≥ 18

Gallstone disease

No significant systemic comorbidities

Exclusion:

Age < 18

Conversion to open surgery

Acute cholecystitis

Prior common bile duct surgery

Presence of diastasis recti or umbilical hernia

4. Surgical Technique

Standard LC using:

10 mm umbilical camera port

10 mm epigastric port

Two 5 mm subcostal ports

Fascial closure was performed only at the umbilical site using polyglactin sutures.

Epigastric port sites were not sutured.

Gallbladder retrieval performed using a bag.

5. Postoperative Management & Follow-Up

Pain Control:

IV paracetamol and tramadol postoperatively. VAS recorded at 6 and 24 hours.

Discharge & Follow-up:

Routine discharge on Day 1 if no complications. All patients followed for 12 months.

Hernia Diagnosis:

Symptomatic patients evaluated with ultrasonography. Asymptomatic patients underwent

scheduled USG at 6 and 12 months.

6. Statistical Analysis

- Data analyzed with SPSS v26 and RStudio.
- Categorical data were analyzed using Fisher's exact or Chi-square tests
- Continuous variables were compared using Student's t-test or Mann–Whitney U test
- Univariate and multivariate logistic regression performed to evaluate TSH risk factors.
- Significance threshold: P < 0.05

7. Results Summary

Demographics:

Age, BMI, and other baseline factors were comparable between groups.

Outcomes:

- Hernia rate: 6 in Group U, 5 in Group E (all at umbilicus)
- Retrieval time shorter in Group E (P = 0.013)
- Pain lower in Group U at 6h (P = 0.027)
- No difference in 24h VAS scores
- Multivariate Analysis:
- Fascial widening was the only independent predictor of TSH (OR = 4.08, P = 0.05)

8. Discussion

- All trocar site hernias (TSH) occurred at the umbilical site, regardless of extraction route.
- This confirms the umbilicus as the most vulnerable location for hernia development after
- laparoscopic cholecystectomy.
- Epigastric extraction avoided direct stress on the umbilical site and was associated with no
- hernias at the epigastric port.
- Gallbladder retrieval was faster via the epigastric route, offering operative efficiency.
- Early postoperative pain (6h) was slightly higher with epigastric extraction but not clinically
- limiting.
- Fascial widening during extraction was the only independent risk factor for TSH.
- These findings support preferential use of the epigastric port for specimen retrieval to
- minimize hernia risk.

9. Conclusion

While trocar site selection did not statistically alter the incidence of hernia, all hernias occurred at

the umbilicus, highlighting its vulnerability. Fascial widening during extraction was a key

modifiable risk factor. Epigastric retrieval may offer operative efficiency, but at a slight cost in

postoperative discomfort.

10. Ethical Considerations

- Approved by the Clinical Research Ethics Committee of Istanbul University of Health
- Sciences, Umraniye Training and Research Hospital.
- All participants provided written informed consent.
- Study conducted in accordance with the Declaration of Helsinki.
- No funding received. No conflicts of interest declared.

STATISTICAL ANALYSIS PLAN (SAP)

Study Title: Umbilical Trocar Site Is the Usual Suspect for Trocar Site Hernia After

Laparoscopic Cholecystectomy: A Prospective Study

Version: 1.0

Prepared by: [name]

Study Sponsor: Umraniye Research and Training Hospital

Principal Investigator: Ass. [name]. [name]

1. Study Overview

This is a prospective, randomized, controlled clinical trial evaluating the incidence of trocar site hernia (TSH) in patients undergoing laparoscopic cholecystectomy, comparing gallbladder extraction via the umbilical versus epigastric port.

2. Study Objectives

Primary Objective:

To assess whether the site of gallbladder retrieval (umbilical vs. epigastric trocar) affects the incidence of trocar site hernia.

Secondary Objectives:

To compare postoperative pain levels at 6 and 24 hours between groups

To assess gallbladder retrieval time

To identify independent risk factors for the development of trocar site hernia

3. Endpoints

Primary Endpoint:

Incidence of trocar site hernia (clinical or ultrasonographic diagnosis within 12 months)

Secondary Endpoints:

- Gallbladder retrieval time (in seconds)
- Visual Analogue Scale (VAS) pain scores at 6 and 24 hours postoperatively
- Occurrence of fascial widening and its association with TSH

• Logistic regression model identifying independent risk factors for TSH

4. Analysis Populations

Intention-to-Treat (ITT):

All randomized patients, excluding those who converted to open surgery or were lost to follow-

up.

Per Protocol (PP):

Patients who completed surgery and 12-month follow-up without major protocol deviations.

5. General Statistical Methods

- Statistical significance threshold set at P < 0.05 (two-sided).
- All statistical analyses will be performed using SPSS v26.0 and RStudio v4.2.0.
- Results will be reported with appropriate confidence intervals (CIs) and effect sizes when
- applicable.

6. Data Handling and Assumptions

Missing Data:

No imputation will be performed.

Patients lost to follow-up will be excluded from analysis of outcomes they did not complete.

Outliers:

Checked visually (boxplots, scatterplots).

No exclusions unless clinically justified.

Normality Testing:

Shapiro-Wilk test used for continuous variables.

7. Baseline and Demographic Comparisons

Descriptive statistics: mean ± SD for normally distributed data; median (min-max) for non-

normal data; frequency (%) for categorical variables.

Comparisons:

• Categorical variables: Chi-square or Fisher's exact test

• Continuous variables: Student's t-test or Mann–Whitney U test depending on distribution

8. Primary Endpoint Analysis

Incidence of TSH:

Compared between the umbilical and epigastric groups using Fisher's exact test.

9. Secondary Endpoint Analyses

- Gallbladder retrieval time: Compared using Mann–Whitney U test (non-normal distribution
- anticipated).
- Postoperative pain scores (VAS at 6h and 24h): Assessed separately at both time points.
- Compared using Mann–Whitney U test.
- Exploratory regression analyses: Univariate logistic regression to identify factors associated
- with TSH Variables with P < 0.2 or known clinical relevance will be entered into a
- multivariate logistic regression model.
- Odds Ratios (OR), 95% CI, and P-values will be reported.

10. Subgroup Analyses

Subgroup analysis will be performed for patients in the umbilical extraction group to evaluate the

impact of fascial widening on TSH incidence using logistic regression.

11. Software

All analyses will be conducted using:

- SPSS v26.0 (IBM Corp., Armonk, NY, USA)
- RStudio v4.2.0 (The R Foundation)

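### The fascial widening result (OR = 4.08, P = 0.05, no confidence interval) is not shown to meet the plan's strict P < 0.05, yet it is stated without qualification as an independent and modifiable risk factor

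*Combined protocol and SAP*

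**What the plan says.** The decision rule is the same in both parts of the document. CSR section 6 gives "Significance threshold: P < 0.05", and SAP section 5 sets the same strict inequality, two-sided. CSR section 6 also records "Univariate and multivariate logistic regression performed to evaluate TSH risk factors". SAP section 9 describes the regression and says that odds ratios will be given with 95% CIs and P-values.

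The result is printed twice:

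- CSR section 1, Key Results: "Fascial widening was the only independent risk factor for TSH (OR = 4.08, P = 0.05").
- CSR section 7, under its multivariate heading: "Fascial widening was the only independent predictor of TSH (OR = 4.08, P = 0.05").

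Neither place gives a CI, and none appears elsewhere.

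The wording then becomes firmer. CSR section 8 says "Fascial widening during extraction was the only independent risk factor for TSH", without the P-value. CSR section 9 says "the umbilicus, highlighting its vulnerability. Fascial widening during extraction was a key" and, across the line break, completes the phrase by calling widening a modifiable risk factor.

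On the data behind the model, CSR section 1 says "100 patients (50 in each group) were included in the final analysis", with 6 hernias in the umbilical group and 5 in the epigastric group. SAP section 10 plans a further logistic regression of widening on hernia within the umbilical extraction group alone.

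**The concern.** A strict threshold of 0.05 and a printed P of 0.05 leave the decision open. The reader cannot tell from the page whether the plan's rule was met, yet four CSR sections write as if it had been. The CI that SAP section 9 promises would show both which side of 1 the lower limit falls and how wide the estimate is.

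The result also cannot be checked. The document does not give the test behind the P, the covariates in the model, or the number of patients with and without widening by hernia status.

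A second fault in the Conclusion does not depend on the P-value. Retrieval site was randomised and fascial widening was not. A regression coefficient for a non-randomised intraoperative event describes an association. Calling it a key modifiable risk factor invites the reader to conclude that avoiding widening would prevent hernias, which this analysis cannot show.

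With the primary comparison null, widening is the only risk factor named in the Conclusion, so readers are likely to take it away from the report.

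**Working it through.** **Inputs**

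- OR = 4.08 and P = 0.05: CSR sections 1 and 7.
- Threshold P < 0.05: CSR section 6; two-sided in SAP section 5.
- 6/50 and 5/50 hernias, so 6 + 5 = 11 in 100 patients: CSR section 1.
- Widening counts, covariates, standard error and test: not given.

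**What can be reproduced.** Fisher's exact test on 6/50 against 5/50 gives P = 1.00, as printed, so the event counts are consistent with the stated primary result. The OR of 4.08 and its P cannot be rebuilt from the document.

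**What the printed P can mean.** Precision in the CSR is not uniform: 1.00 and 0.05 have two decimals, 0.013 and 0.027 have three. So 0.05 could be a two-decimal rounding (0.045 to 0.055) or 0.050 with the last zero dropped (0.0495 to 0.0505). Both ranges contain the threshold.

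**Implied interval.** Assume a two-sided Wald test. Then

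- ln(4.08) = 1.4061
- SE = 1.4061 / z, where z is the two-sided normal quantile for P
- 95% CI = exp(1.4061 ± 1.96 × SE)

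| P | z | SE | Lower limit | Upper limit |
|---|---|---|---|---|
| 0.045 | 2.005 | 0.7014 | 1.032 | 16.13 |
| 0.0495 | 1.964 | 0.7158 | 1.003 | 16.60 |
| 0.050 | 1.960 | 0.7174 | 1.000 | 16.65 |
| 0.0505 | 1.956 | 0.7190 | 0.997 | 16.70 |
| 0.055 | 1.919 | 0.7328 | 0.970 | 17.16 |

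Rounding of the OR itself (4.075 to 4.085) moves the lower limit by 0.0001 or less. The lower limit falls on either side of 1 under both readings of the printed P, and the upper limit is about 16 to 17 throughout.

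**How much the test matters.** Two made-up unadjusted tables, each with 11 hernias in 100 patients and an OR near 4.08, show this. They are not trial data.

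- Hernia in 4/15 with widening and 7/85 without: OR 4.05, Wald P = 0.047, likelihood-ratio P = 0.060.
- Hernia in 8/43 with widening and 3/57 without: OR 4.11, Wald P = 0.047, likelihood-ratio P = 0.034.

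At this boundary the choice of test alone can change the decision, and the direction depends on the counts. The test therefore has to be named.

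**The case against.** **The SAP's own vocabulary.** SAP section 2 makes finding independent risk factors a secondary objective, so the word independent is planned language. This stands. If the unrounded P is below 0.05, the term may remain, provided the CI is shown with it.

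**The Wald assumption.** The test is not stated, and another test would give a different interval. This also stands: the limits above are conditional figures. The undisclosed decimals and the missing CI do not depend on that assumption.

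**The word modifiable.** It can mean only that the exposure is under operative control, and the document does not define widening. That reading is possible. In a Conclusion that calls widening a key risk factor, however, most readers will take the word to mean that changing it changes the hernia risk, so the phrase needs replacing.

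**Stronger readings that a reader might infer.**

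- That the result is non-significant. This does not follow: a rounded 0.05 may stand for a value just below the threshold.
- That the number of hernias per model term can be worked out from the OR. It cannot, because the estimator, covariates and analysis set are not stated.
- That the SAP contradicts itself by listing this analysis as secondary and also labelling the regression exploratory. This is loose labelling: the SAP attaches no different threshold to either label, and no result changes.

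**Conclusion.** The concern holds as a reporting and interpretation fault that should be fixed. As printed, the widening result is not shown to meet the plan's P < 0.05, nor is it shown to fail it. The CI required by SAP section 9 is missing, and the wording in CSR sections 1, 7, 8 and 9 is firmer than the printed figures allow.

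On the Wald assumption the data are compatible with an odds ratio from about 1 (0.97 to 1.03 across the rounding range) to about 16 or 17, which is very imprecise. The causal flavour of the Conclusion is unsupported whatever the P, because widening was not randomised.

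Two things are untouched: the primary comparison, and the observation that all hernias were at the umbilicus.

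**What to change.** From the model actually fitted:

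1. Report P to at least three decimals, or four if it prints as 0.050, with the 95% CI.
2. Name the test and the covariates.
3. State whether the analysis set is the 100 analysed patients or the umbilical subgroup of SAP section 10.
4. Give the numbers with and without widening by hernia status.

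Then apply P < 0.05 to that P:

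- **Not below 0.05:** replace the wording in CSR sections 1, 7, 8 and 9 with a statement that no factor met the threshold, followed by the fascial widening OR of 4.08 and its 95% CI. Since widening is reported as the only factor to qualify, none would remain.
- **Below 0.05:** the SAP's term independent risk factor may stay, shown with its CI.

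In either case, replace the key modifiable risk factor phrase in CSR section 9 with wording that describes an association.

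The cost is a text edit or, if the CI was not kept, one refit of the same model on existing data. No new data are needed. The downside is a weaker stated conclusion.

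### CSR 8 credits epigastric retrieval with a lower hernia risk that the trial's own randomised comparison (6/50 v 5/50) does not show

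*Combined protocol and SAP*

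**What the plan says.** Every patient has a 10 mm umbilical and a 10 mm epigastric port (CSR 4); the arms differ in which one the gallbladder leaves by.

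- **Endpoint.** SAP 3 defines the primary endpoint as "Incidence of trocar site hernia (clinical or ultrasonographic diagnosis within 12 months"), and CSR 1 as "Incidence of trocar site hernia at 12-month follow-up". Neither names a port.
- **Test.** SAP 8: "Compared between the umbilical and epigastric groups using Fisher's exact test". SAP 5: "Statistical significance threshold set at P < 0.05 (two-sided"). SAP 5 also undertakes to report confidence intervals and effect sizes where applicable.
- **Result.** CSR 1 gives 6/50 (12%) against 5/50 (10%), P = 1.00, and adds "All hernias were located at the umbilical site". CSR 7 repeats it: "Hernia rate: 6 in Group U, 5 in Group E (all at umbilicus").
- **Discussion.** CSR 8 first says that the hernias were umbilical whichever route was used. It then says "Epigastric extraction avoided direct stress on the umbilical site and was associated with no" hernias at the epigastric port. Its last bullet says that the findings favour the epigastric port for retrieval in order to keep hernia risk down.
- **Conclusion.** CSR 9 says that the choice of site did not statistically change hernia incidence.

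**The concern.** CSR 8 attributes the absence of epigastric-port hernias to epigastric extraction. An association needs a comparison, and the relevant one is the same port in the arm that did not extract through it. That count was also zero. The other half of the bullet, that the umbilicus was spared stress, should show as fewer umbilical hernias in Group E if it mattered for the outcome; the counts were 6 and 5.

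The closing bullet then turns this into a preference for one route on grounds of hernia risk. That is the question the trial randomised patients to answer, and its answer was no detectable difference. A reader who takes the message from CSR 8 leaves with a different conclusion from one who reads CSR 9. No interval is given for the difference, so neither reader can see how little 11 events settle.

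**Working it through.** **Inputs.** "100 patients (50 in each group) were included in the final analysis" (CSR 1). Hernias: 6 in Group U and 5 in Group E, all umbilical (CSR 1, CSR 7). Two-sided 0.05 (SAP 5). Fisher's exact test (SAP 8).

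**1. The reported P value.** Table [[6, 44], [5, 45]]. With 11 events and equal arms, 6 v 5 is the most even split possible. Every other split is at most as probable, so the two-sided Fisher P is 1.00. This reproduces CSR 1.

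**2. Hernias by port and arm.** Since all 11 were umbilical, the epigastric counts follow by subtraction.

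| Port | Group U | Group E |
|---|---|---|
| Umbilical | 6/50 | 5/50 |
| Epigastric | 6 - 6 = 0/50 | 5 - 5 = 0/50 |
| Any port, per patient | 6/50 | 5/50 |

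The umbilical row and the any-port row are the same table, so both have P = 1.00.

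**3. Interval for the umbilical (and any-port) difference.** Difference = 0.12 - 0.10 = 0.02. Wilson 95% limits: 6/50 gives 0.0562 to 0.2380; 5/50 gives 0.0435 to 0.2136. Newcombe's method:

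- lower = 0.02 - √[(0.12 - 0.0562)² + (0.2136 - 0.10)²] = -0.110
- upper = 0.02 + √[(0.2380 - 0.12)² + (0.10 - 0.0435)²] = 0.151

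The difference is 2.0 points, 95% CI -11.0 to 15.1. The data are compatible with appreciably fewer or appreciably more hernias under epigastric retrieval.

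**4. What the epigastric zero shows.** Clopper-Pearson upper limit for 0/50: 1 - 0.025^(1/50) = 0.071, or 7.1%, in each arm. The observed difference between arms is 0. The zero limits how common epigastric-port hernia is likely to be under either route, but gives no contrast between routes.

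**5. CSR 8 beside CSR 9.** CSR 8's last bullet presents lower hernia risk as supported by the findings. CSR 9 says that incidence did not differ statistically by site. Steps 1 to 3 agree with CSR 9.

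**The case against.** **The null result is disclosed.** CSR 8's first bullet and CSR 9 both tell the reader that route did not separate the arms. That stands: the reported primary conclusion is not reversed. It does not rescue the last bullet, which gives hernia risk as the reason for preferring a route.

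**The zero can be a safety observation.** CSR 4 says that epigastric ports were not sutured, so no hernia at an unsutured port used for extraction is worth recording. This also stands, within the 7.1% limit. It is an observation about one port, not evidence that route lowers a patient's hernia risk. Likewise, sparing the umbilicus may be meant only as a description of technique; the trial neither shows nor excludes a benefit from it.

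**The recommendation may rest on fascial widening.** CSR 8 also lists widening (OR 4.08, P = 0.05) and retrieval time. Retrieval time is not a hernia outcome. Any effect of route through widening is already contained in 6/50 v 5/50, and the documents give no widening counts by arm.

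**A stronger reading a reader might infer.** Because SAP 3 and SAP 8 name no port, one could suppose that the primary endpoint is undetermined between hernia at any port and hernia at the retrieval port, and that CSR 8 argues from the second. The retrieval-port table would be 6/50 v 0/50, with two-sided Fisher P = 2 × C(50,6)/C(100,6) = 0.027. It compares a different anatomical site in each arm and drops the five Group E hernias. With no route effect, zero epigastric risk and umbilical risk of 8% to 12%, it would reject 21% to 56% of the time. These are this review's hypothetical calculations. No document plans, tabulates or runs that test, and CSR 8 never sets its zero against 6/50. CSR 1 and CSR 7 settle the definition in use, because they count five Group E hernias that were not at that arm's retrieval port. The P = 0.027 printed in the CSR is for 6-hour pain; the match is coincidence.

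**Conclusion.** The concern holds as a fault in CSR 8's inference. Same port against same port, the arms differ by 6/50 v 5/50 at the umbilicus (2.0 points, 95% CI -11.0 to 15.1, P = 1.00) and by 0/50 v 0/50 at the epigastrium. Neither supports saying that epigastric retrieval lowers hernia risk, and the interval does not exclude an effect in either direction. CSR 8's last bullet also conflicts with CSR 9.

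The unnamed port in SAP 3 and SAP 8 is a missing detail only; supplying it changes no reported figure.

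Assumptions: the 100 analysed patients are taken as the comparison, although 110 were randomised; each hernia is counted once per patient; and the statement that all hernias were umbilical is taken at face value, since the documents do not say which port sites were scanned.

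**What to change.** 1. **CSR 8, epigastric-port bullet.** Replace with: *No epigastric-port hernia occurred in either arm (0/50 v 0/50); umbilical hernia was 6/50 v 5/50 (difference 2.0 points, 95% CI -11.0 to 15.1), so the trial shows no detectable effect of retrieval route and does not exclude one in either direction.*
2. **CSR 8, last bullet.** Reconcile it with CSR 9 and this interval, so that lower hernia risk is not stated as a finding of the trial. Changing only the bullet in item 1 would leave the unsupported claim in place.
3. **CSR 7.** Add the port-by-arm table, labelled descriptive, comparing each port with the same port in the other arm. Give the interval beside the primary P value, as SAP 5 undertakes.
4. **SAP 3 and SAP 8 (minor).** State that the endpoint is at least one hernia at any trocar site, per patient, within 12 months. Mark this as a post hoc clarification, since results are known.

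Cost: wording and one small table, with no new data and no change to the primary P value. The CSR loses one argument for epigastric retrieval; its findings on retrieval time and pain are untouched.

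### The CSR calls the extra 6-hour pain slight and not limiting, and the faster retrieval efficient, without reporting the size of either effect

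*Combined protocol and SAP*

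**What the plan says.** SAP section 3 lists one time endpoint, "Gallbladder retrieval time (in seconds"), and one kind of pain endpoint, VAS at 6 and 24 hours. SAP section 9 compares each by the Mann-Whitney U test. SAP section 5 adds that "Results will be reported with appropriate confidence intervals (CIs) and effect sizes when" applicable.

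CSR section 1 gives the findings as "Epigastric retrieval was faster (P = 0.013) but associated with more early pain (P = 0.027"). CSR section 7 repeats them in the same form, for example "Retrieval time shorter in Group E (P = 0.013"), and says without a figure that 24-hour VAS did not differ.

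CSR section 8 then interprets them. On time: "Gallbladder retrieval was faster via the epigastric route, offering operative efficiency". On pain: "Early postoperative pain (6h) was slightly higher with epigastric extraction but not clinically" limiting. CSR section 9 is softer: "Epigastric retrieval may offer operative efficiency, but at a slight cost in" postoperative discomfort.

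**The concern.** Words such as *slight* describe a size, and no size is reported for pain at either time point. To say that pain was not limiting is to make a statement about a further outcome. The documents define no such outcome: no measure of function, mobilisation, analgesic use or delayed discharge, and no VAS difference named as clinically relevant. Analgesia and discharge on Day 1 appear in CSR section 5 only as routine management.

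The efficiency statement has a narrower gap. Retrieval was timed and was faster, but it is one step of the operation, and total operative time is not among the endpoints.

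The stake is what a reader takes from the secondary results. The hernia comparison shows no difference between the arms (6/50 against 5/50, P = 1.00). Time and early pain are the only outcomes on which the CSR reports that the arms differ. The closing text presents one as a benefit and the other as minor, and the reader has no figures with which to judge that balance.

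**Working it through.** **Inputs.** CSR section 1 gives the analysed set: "100 patients (50 in each group) were included in the final analysis". The P-values are 0.013 (retrieval time) and 0.027 (6-hour VAS), from CSR sections 1 and 7. SAP section 5 makes tests two-sided, and SAP section 9 specifies Mann-Whitney for both outcomes.

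**What can be reproduced.** The two P-values cannot be recomputed, because no summary data are given. As a check on the denominators, Fisher's exact test on 6/50 against 5/50 gives P = 1.00, as stated.

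**What the P-values imply.** Inverting them shows how much the reported results can tell a reader.

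- Two-sided z: 2.484 for P = 0.013 and 2.212 for P = 0.027.
- Null standard error of the Mann-Whitney probability: sqrt((n1 + n2 + 1) / (12 × n1 × n2)) = sqrt(101 / 30,000) = 0.0580.
- Probability of superiority = 0.5 + z × SE, with approximate 95% limits ± 1.96 × 0.0580 = ± 0.114.
- Normal-equivalent d = sqrt(2) × inverse normal of that probability.

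| Outcome | Probability of superiority (approx. 95% CI) | d |
|---|---|---|
| Retrieval time | 0.5 + 2.484 × 0.0580 = 0.644 (0.53 to 0.76) | 0.52 |
| 6-hour VAS | 0.5 + 2.212 × 0.0580 = 0.628 (0.51 to 0.74) | 0.46 |

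**Sensitivity.**

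- Ties in VAS: if they cut the null variance to 0.8 of its untied value (an assumption), the pain figure becomes 0.5 + 2.212 × 0.0580 × sqrt(0.8) = 0.615.
- t-test instead, since CSR section 6 does not say which test was used for which outcome: d = t × sqrt(2/50), so 2.530 × 0.2 = 0.51 (0.11 to 0.90) for time and 2.245 × 0.2 = 0.45 (0.05 to 0.85) for pain.
- Separating the two effects: the z values differ by 2.484 − 2.212 = 0.272. The standard error of that difference is sqrt(2 − 2ρ), which is 1.0 to 1.6 for assumed correlations of 0.5 to −0.3. The results neither separate the two standardised effects nor show them to be equal.

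**What the P-values cannot give.** Original units would need standard deviations, which the documents do not report. If the VAS standard deviation were 1 to 2.5 points (assumed), d = 0.45 would be about 0.4 to 1.1 points. If the standard deviation of retrieval time were 30 to 120 seconds (assumed), d = 0.51 would be about 15 to 61 seconds. These ranges only illustrate the uncertainty and are not estimates.

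**The case against.** The case for the CSR has four parts.

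1. *Retrieval time is a legitimate measure.* It is a listed endpoint. Allocation was revealed just before extraction, so this is the step at which the arms begin to differ. Total operative time would mostly add dissection that allocation cannot affect. This stands. A reader might infer that the trial measured nothing bearing on efficiency, and the documents do not support that. Only the breadth of the word is open to criticism, and the CSR 8 sentence itself opens by naming retrieval.

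2. *Similar standardised effects do not contradict the adjective.* A reader might take 0.64 and 0.63 to mean that the pain cost is as large as the time gain, so that *slight* is wrong. That does not follow. The similarity depends on the assumed test and on about 50 per arm, the intervals are wide, and a standardised effect in seconds is not comparable in clinical importance with one in VAS points. This stands in full.

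3. *The 24-hour result points to short-lived pain.* It is relevant and belongs in the account. But it has no estimate or interval, so it reports only that no difference was detected. It also does not show that pain at 6 hours was not limiting.

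4. *The conclusion is hedged and the plan is conditional.* CSR 9 says only that efficiency may be gained, openly names a cost, and does not repeat the claim about limitation. SAP 5 is qualified by *when applicable*. Both are true. Yet a difference with an interval plainly applies to a two-arm comparison of seconds or VAS scores. CSR 9 still sizes the cost with no figure behind it.

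CSR 8's recommendation of the epigastric port is argued on hernia risk, so correcting the time and pain wording would leave that recommendation untouched.

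**Conclusion.** The point holds as one of unsupported interpretation and incomplete reporting. CSR 8 describes the 6-hour pain as slightly higher and not limiting, and CSR 9 calls it a slight cost. Behind this are two P-values, one unquantified statement of no difference, and no limitation outcome or relevance threshold. The efficiency wording goes beyond the one step that was timed.

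The statements are unsupported rather than refuted. The pain difference may well be small in VAS points, but the documents do not let a reader tell. The implied probabilities of superiority, 0.644 and 0.628, assume Mann-Whitney tests, 50 per arm and no ties. They show only that the reported evidence gives no statistical ground for treating one effect as a benefit and the other as minor. The choice of tests and the primary hernia comparison are not in question.

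**What to change.** - **CSR 1 and 7:** report medians by arm and the Hodges-Lehmann difference with its 95% confidence interval for retrieval time in seconds and for VAS at 6 and 24 hours. State the VAS range used, which the documents do not give.
- **SAP 9:** if these estimates are added, label them post hoc, because the results are already known.
- **CSR 8:** delete the statement that pain was not clinically limiting. Replace *slightly* with the estimated 6-hour difference and its interval. Say that no difference was detected at 24 hours, and give that interval too.
- **CSR 9:** replace *slight* with the same 6-hour estimate.
- **CSR 8 and 9:** confine operative efficiency to a shorter retrieval step.

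The claims should not be rescued with a total operative time comparison or a VAS threshold chosen now. Neither is in the plan, and both would be selected after the results.

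The cost is three interval estimates from data already collected and a few changes of wording. The downside is a somewhat less favourable closing message for epigastric retrieval.
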